An eHealth intervention to increase depression treatment initiation and adherence among veterans referred for mental health services (CDA 18-189)

NCT05990075

November 30, 2022

*Analysis plan:*

*Data processing.* Data will be checked for out of range values and missing data where appropriate through plotting and descriptive analyses. Finally, data will be transformed as needed to create the variables of interest (e.g. age of depression onset as age of first episode visible in the EHR). *Missing Data Strategies.* We will minimize the level of missing data (due to loss to follow-up, withdrawal, or missing assessments) to the extent possible. If missing data occur, I will assess the missing data mechanism for data missing due to loss to follow-up or withdrawal. I will compare baseline measures (e.g., demographics, clinical history, etc.) between subjects that have complete outcome data and those that do not using logistic regression. Multiple imputation will be used for missing data in conjunction with a pattern of missingness. Missing data will be evaluated on an ongoing basis and recruitment may be continued beyond the original sample to achieve the desired power for the proposed analyses. *Data Analysis.* First, descriptive analyses will be performed on all baseline patient characteristics extracted for all patients approached for study enrollment, including those who agreed and did not agree to participate. To compare these two groups, we will use student t-tests (for continuous variables) and chi-square analysis (for categorical variables). This information will be used to derive acceptability of the proposed intervention. Next, descriptive analyses will be performed on the baseline questionnaires collected from the group of participants enrolled. This will give us additional data about patient characteristics that may further refine our phenotypes or improve study feasibility in the future. Feasibility will be derived from percentage of prompts completed per days of participation in the intervention. Finally, we will calculate rates of treatment initiation (and corresponding 95% confidence interval) and compare to the initiation rate identified in the literature. To compare study treatment initiation to rates we will calculate the 95% confidence interval (CI) for the difference score between proportions (see Franklin, 2007). A significant difference will be denoted if the 95% CI does not include zero (Cumming & Finch, 2005).

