- Potentially temporary states/situations that may significantly impair mood/capability to engage in treatment: unstable environment that is not in one's control (e.g., homeless, temporary group home, extensive care taking duties).

Sampling plan: The target population is a clinical sample of Veterans with depression who meet the criteria in Table 2. Exclusion criteria are consistent with conventional depression studies. Veterans will be excluded if they have a medical disorder that would significantly increase their risk of depression secondary to a medical diagnosis or due to treatments for those medical diagnoses (e.g., cardiovascular disease; SUD) or those experiencing side effects with standard treatment or would require a significant adaptation of treatment (e.g., bipolar disorder). Veterans will also be excluded consistent with the standard of care for cognitive and/or behavioral treatment of depression at Tampa VA (e.g., actively suicidal patients that need intensive and immediate treatment). Patients will need to have a risk score associated with lack of treatment initiation as determined in Aim 1.

Recruitment: The Tampa VA is an ideal site because it has a large and diverse mental health population. In FY17 over 2000 patients had a first visit to primary and specialty mental health care, with over half showing a depression diagnosis in their charts. Veterans will be recruited using the following methods: 1) Depression treatment consults. Veterans referred for mental health treatment (psychotherapy or medication) through the mental health consult service will be informed about the proposed CDA clinical trial either by their provider or the study RA who will regularly monitor MH referrals on CPRS. 2) Advertisement. IRB-approved brochures will be placed throughout Tampa VA (e.g., primary care, pharmacy). Interested Veterans can contact study staff to learn more about participating. 3) Referrals from providers. Tampa VA providers in primary care - mental health service lines will be informed of the study and given research brochures. Providers can then give information to Veterans referred to specialty care for treatment.

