#### **A4c. Aim 3.**

**Study/Design Overview:** Aim 3 will focus on completing phase 2 of the eHealth intervention development, which will be a formative evaluation. For this portion of the study we will collect both qualitative and quantitative data from a new sample of patients using same inclusion/exclusion criteria in Table 2. This portion of the study will help to determine usability, acceptability, engagement with the intervention, and potential problems with completing the intervention and collecting data in a complete and rigorous manner.

Participant recruitment and sampling: Participant recruitment and sampling will follow steps described in Aim 2. The sample size selected for this aim (n=15) is in line with samples recommended for formative evaluations and pilots. The sample is attainable based on rationale presented in Aim 2. The analytical rationale for the sample size is based on the proposed analyses presented below.

Procedures: Veterans recruited for this aim will be asked to complete 1) baseline questionnaires to understand the clinical make-up of the sample and unobserved patient characteristics that may impact our formative evaluation findings, 2) the intervention, and 3) a semi structured interview to complete the formative evaluation.

Self-report measures: These quantitative measures will be used to better understand the makeup of our sample in terms of clinical characteristics and treatment readiness that may not otherwise be observable from the structured data in their EHRs: **Patient Health Questionnaire 9 (PHQ-9)**, 9-item instrument that assesses the symptoms of depression corresponding to the Diagnostic and Statistical Manual Version 5 (DSM-5) diagnostic criteria for a major depressive episode. Item responses are on a four-point scale (from occurring “not at all” to “nearly every day” over the past two weeks) resulting in a score range from 0 to 27. The PHQ-9 has similar psychometric properties to other measures of depression. PHQ-9 is favored for its brevity and ease of use in clinical settings (Cameron et al, 2011).

**Posttraumatic Stress Disorder Check List for DSM-5 (PCL-5)**, 20-item self-report of the severity of PTSD symptoms in the past month using a 5-point scale (0-4), ranging from “Not at all” to “Extremely.” A cut-point of 50 (range 0-80) represents a probable diagnosis of PTSD.

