*Data Analysis. First, descriptive analyses will be performed on all baseline patient characteristics extracted for all patients approached for study enrollment, including those who agreed and did not agree to participate. To compare these two groups, we will use student t-tests (for continuous variables) and chi-square analysis (for categorical variables). This information will be used to derive acceptability of the proposed intervention. Next, descriptive analyses will be performed on the baseline questionnaires collected from the group of participants enrolled. This will give us additional data about patient characteristics that may further refine our phenotypes or improve study feasibility in the future. Engagement will be derived from percentage of prompts completed per days of participation in the intervention. Finally, we will calculate rates of treatment initiation (and corresponding 95% confidence interval) and compare to the initiation rate identified in our recent study on the Aim 1 cohort. To compare study treatment initiation to rates observed in Aim 3 to those in Aim 1 sample we will calculate the 95% confidence interval (CI) for the difference score between proportions (see Franklin, 2007). A significant difference will be denoted if the 95% CI does not include zero (Cumming & Finch, 2005). I will use negative binomial regression which accounts for overdispersion if treatment initiation is low (Coxe, West, & Aiken, 2009).*

Qualitative interviews and analysis: The interviews will be conducted using a semi-structured interview guide (see Appendix 3) and the same methods as Aim 2 interviews and analysis. These interviews will focus on the user's experiences using the self-monitoring intervention. Feedback will be sought about the functionality of the intervention, its perceived use, and ways to enhance it. We will specifically inquire about patients' perceptions about the three parts of the intervention: the symptom self-monitoring, practical support (i.e., appointment reminders), and emotional support (i.e., encouragement). Patients will also be asked to provide suggestions for emotionally supportive messages patients may want to see as they prepare to attend mental health sessions. Qualitative data will be analyzed in the same manner as presented in Aim 2.

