**Future Project 1** (proposed HSR&D Merit in CDA year 3). An initial HSR&D Merit will be an efficacy/effectiveness RCT testing whether the eHealth intervention developed and piloted in the current CDA increases treatment initiation and adherence with a focus on treatment outcomes. The proposed RCT will be enhanced through a study design that includes both an active (i.e., engaging with technology) and passive control group (treatment as usual which entails waiting between referral and treatment initiation), more robust sample sizes, and if deemed appropriate, a pre-implementation qualitative aim designed to more thoroughly investigate implementation barriers and facilitators. Outcomes of the proposed Merit will include treatment initiation and adherence, as well as depression outcomes, such as increased awareness of depression, higher depression knowledge, and clear identification of treatment goals. **Future Project 2**. Although we are no longer using NLP in the proposed CDA, we have submitted an HSR&D Pilot and received promising feedback that indicates that a Merit is warranted. I will be revising this application with reviewer feedback and develop it into another HSR&D Merit. The proposed study will employ NLP to develop methods that reliably extract routinely reported patient characteristics by mental health care providers in clinical notes, as a promising route to identifying a clinical marker for treatment engagement and depression outcomes. We will develop the NLP system to determine consistency and variability of documentation across providers and facilities. These data will enable an examination of the value of this clinical marker for depression outcomes.

My proposed CDA and future projects represent the next stage in developing my program of research to implement behavioral treatments for depression within primary care settings in the VHA. The proposed research will also help to move the field of depression research forward by contributing to our understanding of depression management; it could result in new mental health care models for depression, decrease disease burden, and fill the gap in the current depression treatment guidelines.

Table 3. Timeline of CDA Research Activities (Years 1-5).

Research Activity*	Quarters	Year 1				Year 2				Year 3				Year 4				Year 5			
		1	2	3	4	1	2	3	4	1	2	3	4	1	2	3	4	1	2	3	4
Aim 1																					
IRB, R&D, train RA																					

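### The pilot's treatment-initiation rate is tested against an outside rate, although consent selection of unknown direction and size can move that comparison with no intervention effect

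*SAP*

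**What the plan says.** The SAP (Data Analysis) starts with "all baseline patient characteristics extracted for all patients approached for study enrollment, including those who agreed and did not agree to participate". Agreers and non-agreers are compared by t-test and chi-square, and the stated purpose is narrow: "This information will be used to derive acceptability of the proposed intervention". For the outcome, the SAP says: "Finally, we will calculate rates of treatment initiation (and corresponding 95% confidence interval) and compare to the initiation rate identified in the literature". The Protocol (A4c, Aim 3, Data Analysis) has the same structure but would "compare to the initiation rate identified in our recent study on the Aim 1 cohort". Both documents call the difference significant when its 95% CI excludes zero.

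Neither document says outright that initiation is read only in enrolled Veterans. I infer it from the reference to the study's own initiation rate and from the absence of any plan to follow decliners' outcomes.

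Other relevant text:
- **Sample size.** Protocol A4c: "The sample size selected for this aim (n=15) is in line with samples recommended for formative evaluations and pilots". No target rate, precision or power is given.
- **Recruitment.** Aim 3 follows Aim 2. One route runs through the provider or "the study RA who will regularly monitor MH referrals on CPRS"; another is advertisement, where interested Veterans contact staff (A4b).
- **Entry rule.** Patients must have a risk score associated with not initiating treatment (A4b, Sampling plan).
- **Outcome.** Aim 1 defines initiation from charted encounters with a depression diagnosis (A4a), so it can be read without participation.
- **Later use.** A7 proposes an RCT "testing whether the eHealth intervention developed and piloted in the current CDA increases treatment initiation and adherence", with active and passive control groups.

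**The concern.** The outcome is whether a Veteran takes up offered care. Entry to Aim 3 requires accepting another offer: a phone screen, a face-to-face consent session and daily prompts. The two kinds of willingness may well be related. Nobody in the Aim 1 cohort had to agree to anything, because it is a retrospective record extract, and the documents do not suggest that a literature rate would come from consenters. Matching the outside rate better on severity, referral or time window would not remove this difference.

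The planned agree/decline comparison covers baseline characteristics only, so it cannot show whether agreers and decliners differ in initiation. The plan also goes beyond description: it attaches a significance rule to a comparison that can differ from zero for reasons unrelated to the intervention. At stake is how the Aim 3 initiation result is read when the RCT is prepared.

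**Working it through.** There is no planned figure to reproduce: n=15 rests on precedent, and neither document states the reference rate. What follows is an illustration.

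**Inputs from the documents.** n=15 (Protocol A4c). Aim 1 cohort N=88,456 (Protocol A4a). 18.5% to 27% use of any mental health care among Veterans (Protocol A1), taken as a stand-in for the unstated reference rate p0.

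**Assumptions.** Agreement share a = 25%, one third or 50%. Odds ratio (OR) of initiating, agreers against decliners, 1.5 to 3, and the inverses. All approached initiate at p0, and the intervention has no effect.

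**Step 1: shift from selection alone.** Solve for the agreers' rate pA and the decliners' rate pD:

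a·pA + (1−a)·pD = p0, with pA/(1−pA) = OR·pD/(1−pD).

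Check for p0=27%, a=1/3, OR=2: pA=36.4%, pD=22.3%. Then 0.364/3 + 0.223×2/3 = 0.121 + 0.149 = 0.270. The odds are 0.364/0.636 = 0.572 and 0.223/0.777 = 0.287, a ratio of about 2.

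| p0 | OR | Smallest shift (a=50%) | Largest shift (a=25%) |
|---|---|---|---|
| 27% | 1.5 to 3 | pA=31.0%, +4 points | pA=44.6%, +18 points |
| 18.5% | 1.5 to 3 | pA=21.5%, +3 points | pA=32.5%, +14 points |
| 27% | 1/1.5 to 1/3 | pA=23.0%, −4 points | pA=13.3%, −14 points |
| 18.5% | 1/1.5 to 1/3 | pA=15.5%, −3 points | pA=8.5%, −10 points |

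**Step 2: effect on the significance rule.** I assume a Wald interval for the difference, SE = √[p(1−p)/15 + p0(1−p0)/88,456].

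- p0=27%: at 8/15 (53.3%), SE=0.129 and the lower limit is 0.533−0.27−1.96×0.129 = +0.01. At 7/15 the lower limit is −0.06. The rule first declares an increase at 8/15.
- p0=18.5%: by the same calculation, it first declares an increase at 7/15.

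The binomial chance of reaching the threshold with no intervention effect is:

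| p0 | Threshold | No selection | OR 1.5 to 3, a=25% to 50% |
|---|---|---|---|
| 27% | 8/15 | 2.7% | 6% to 33% |
| 18.5% | 7/15 | 1.2% | 3% to 18% |

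**Step 3: can the all-approached rate separate selection from effect?** Suppose there is no consent selection, the untreated rate is 15%, one third agree, and the intervention raises agreers to 51%. All approached then initiate at 0.51/3 + 0.15×2/3 = 0.17 + 0.10 = 27%. This equals the assumed reference, although the enrolled excess is entirely effect.

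**Step 4: precision of enrolled minus declined.** For an illustrative 6/15 against 6/30, the 95% half-width is 1.96×√(0.4×0.6/15 + 0.2×0.8/30) = 0.29, or 29 points.

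**The case against.** The strongest reply is that Aim 3 is formative. Its stated purposes are usability, acceptability and engagement, the controlled test is reserved for the RCT, and A7 does not say that the pilot rate will size that trial. This stands and limits the weight of the point. It does not justify the significance rule, which is in the plan regardless.

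Four stronger readings are tempting, and the documents do not support them:

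- **That selection must inflate the enrolled rate.** The direction is unknown. Some decliners may already be getting into care. The entry rule also admits only Veterans at risk of not initiating, whereas the Aim 1 reference is the whole PHQ9 ≥ 10 cohort. That pushes the enrolled rate down.
- **That decliners' outcomes are already in hand.** Only their baseline characteristics are planned. Reading later encounters of people who declined research is a new extraction. The IRB exemption in A4a concerns the Aim 1 data.
- **That decliners form a control group.** Eligibility is checked at the phone screen, which decliners may never reach. First contact can be by mail, so refusal and non-response blur. Veterans who start care before they could enrol are likely to fall into the non-enrolled group.
- **That pooling everyone approached diagnoses selection or improves precision.** The pooled rate includes treated Veterans (Step 3), and a narrower interval around it describes a different quantity.

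**Conclusion.** The point holds in a limited form. The planned comparison can differ from zero through consent selection alone, and nothing in the plan would show this. Under the stated assumptions the shift is +4 to +18 points from 27% or about +3 to +14 from 18.5%, with shifts of similar order downward if selection runs the other way. With no effect, the significance rule would declare an increase 6% to 33% of the time instead of 2.7% (base 27%).

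These figures rest on assumed agreement shares and odds ratios, a Wald interval, and a base rate that describes any mental health care use, not initiation after referral. That the rate covers enrolled Veterans only is an inference.

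A reader might conclude that decliners' data would let the pilot separate willingness from effect. They would not: enrolled minus declined mixes selection, eligibility differences and effect, and it is imprecise. The gain is a visible caveat at low cost, which suits a formative pilot.

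**What to change.** In the SAP (Data Analysis) and Protocol A4c:

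1. State in whom treatment initiation is read.
2. For Veterans approached through the referral-list route, extract initiation from the record with one definition and one window for everyone. Aim 1 uses 3, 6 and 12 months; Aim 3 names none.
3. Count from a common date, such as referral or first contact, and report initiations before enrolment separately.
4. Report rates with 95% CIs for enrolled, declined and all approached, keeping non-responders apart from refusers.
5. Present these rates, and any comparison with an outside rate, as descriptive. Remove the significant-difference reading, and do not use the all-approached rate as a test of selection against effect.
6. State that enrolled minus declined mixes selection, eligibility differences and effect, and that only the concurrent control in the later RCT can separate them.

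**Cost.** A short SAP revision and some further record fields, with no additional patient contact. The main condition is that approval must extend to decliners' later encounters. Restricting the report to the referral-list route leaves out Veterans who enrol through advertisement, so its enrolled group may be smaller than 15. If approval is not obtained, items 1 and 5 can still be done for the enrolled group, with consent selection stated as a limitation.

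### If decliners differ from the 15 planned agreers in both number and spread, the pooled t-test can be liberal or conservative; Welch's test with confidence intervals would avoid this cheaply

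*SAP*

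**What the plan says.** The SAP's Data Analysis paragraph begins with description: "descriptive analyses will be performed on all baseline patient characteristics extracted for all patients approached for study enrollment". Agreers and decliners are both covered. It then states that "we will use student t-tests (for continuous variables) and chi-square analysis (for categorical variables"). The protocol has the same sentence under A4c, Aim 3, Data Analysis: "To compare these two groups, we will use student t-tests (for continuous variables) and chi-square analysis (for categorical variables"). Neither document names an unequal-variance version, an effect size or a confidence interval for this comparison.

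The number of agreers comes from the protocol, A4c: "The sample size selected for this aim (n=15) is in line with samples recommended for formative evaluations and pilots". It is a plan and not a ceiling, since the SAP's missing-data text says "recruitment may be continued beyond the original sample to achieve the desired power for the proposed analyses". No expected number of decliners, agreement rate or SD is given.

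Both documents say the comparison feeds into acceptability. Among the Aim 3 measures, the protocol defines acceptability by how many agree to take part, together with enrollment factors. The one stated significance rule, "A significant difference will be denoted if the 95% CI does not include zero", belongs to the treatment-initiation rate.

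**The concern.** Student's t-test estimates one common variance. When the SDs differ, the larger group dominates that estimate, so the standard error of the mean difference is too small if the smaller group has the larger SD and too large if it has the smaller SD. Nothing in the plan balances the two groups: one is planned at 15 and the other is however many decline. Self-selected groups may also differ in spread.

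What is at stake is the account of who accepts the intervention. These tests are the only named method for the enrollment-factors part of acceptability. A difference in, say, age or baseline severity could be flagged too readily or missed, and that reading could carry into recruitment planning for the later RCT. Separately, with about 15 agreers, a bare non-significant p-value could be taken to mean that the groups are alike.

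**Working it through.** **Inputs.** From the documents: Student's t-test (SAP and protocol A4c) and n1 = 15 agreers (protocol A4c). Assumed, because the documents do not give them: n2 = 5 to 135 decliners (agreement from 15/20 = 75% down to 15/150 = 10%), SD ratio r (agreers/decliners) from 0.5 to 2, normal data, two-sided 5%. The plan states no power or error rate for this comparison, so there is no figure of its own to reproduce.

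**Mechanism.** Set the decliners' SD to 1.

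- True variance of the mean difference: r²/n1 + 1/n2.
- Variance the pooled test uses, on average: [((n1 − 1)r² + (n2 − 1)) / (n1 + n2 − 2)] × (1/n1 + 1/n2).

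Four cases:

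- 15 v 30, r = 2: true 4/15 + 1/30 = 0.300; used (14×4 + 29)/43 × 0.1 = 0.198. The standard error is √(0.198/0.300) = 0.81 of what it should be, so the test is liberal.
- 15 v 30, r = 0.67: true 0.449/15 + 1/30 = 0.0633; used (14×0.449 + 29)/43 × 0.1 = 0.0821. The standard error is √(0.0821/0.0633) = 1.14 times too large, so the test is conservative.
- Equal sizes, any r: both expressions reduce to (r² + 1)/n.
- r = 1, any sizes: both expressions equal 1/n1 + 1/n2.

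Both inequalities are therefore needed.

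**Simulated type I error of Student's t** (no true difference, nominal 5%, 15 agreers, 200,000 replicates per cell):

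| Decliners | r = 0.5 | 0.67 | 1 | 1.5 | 2 |
|---|---|---|---|---|---|
| 5 | 15.7% | 10.5% | 5.1% | 2.0% | 1.0% |
| 15 | 5.3% | 5.1% | 5.0% | 5.1% | 5.2% |
| 30 | 1.9% | 2.7% | 5.0% | 8.6% | 11.2% |
| 60 | 0.5% | 1.4% | 5.0% | 12.2% | 18.2% |
| 135 | 0.1% | 0.8% | 4.9% | 15.5% | 24.6% |

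Welch's test stayed between 4.9% and 5.6% in every scenario, highest with 5 decliners. The direction of the pooled test's error reverses when decliners are the smaller group.

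**Power and detectable difference, 15 v 30, equal SDs.** The noncentrality is d × √(15×30/45) = d × 3.162. Power of 80% at two-sided 5% on 43 degrees of freedom needs about 2.87, so d = 2.87/3.162 ≈ 0.91 SD. Power for a 0.5 SD difference is about 34%. At the 80% point Welch's test has 78.8% against 80.0%, a loss of about 1 point.

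**Categorical variables.** The expected count among agreers is 15p, below 5 whenever overall prevalence p is under 5/15 = one third. In a check at prevalences of 5-20%, chi-square ran at about 3.4-6.2%, so little harm was shown.

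**The case against.** The strongest reply is that a conventional two-sample t-test for a descriptive baseline table is not an error. No alpha, hypothesis or decision rule is attached to it, so there is no promised 5% for the test to miss. Neither condition for trouble can be shown from the documents: the decliner count and the SDs are absent. Agreers and decliners come through the same recruitment channels under the same eligibility criteria, which gives no particular reason to expect an SD ratio as large as 2. At 15 against 15, even that ratio leaves the error at 5.2%.

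All of this stands, and it limits the point to a conditional one. It also rules out three stronger readings that a reader might infer:

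- *Unequal group sizes alone break the test.* They do not. With equal SDs it stays at 4.9-5.1% from 5 to 135 decliners.
- *Decliners will outnumber agreers.* No agreement rate is given, and recruitment may go beyond 15.
- *The acceptability result is distorted.* The agreement rate uses no t-test, and the documents do not say that non-significance will be read as similarity.

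The reply does not show that Student's test is the better choice. The plan commits to this comparison and gives it a use, and Welch's test does about as well where the pooled test is sound and better where it is not.

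**Conclusion.** The point holds as a small, inexpensive improvement and not as an error in the plan. The pooled test is vulnerable only if group sizes and SDs both differ. For assumed decliner counts of 30 to 60 and SD ratios of 0.67 to 2, its error runs from about 1% to about 18%. The range is wider at the more extreme assumptions in the table, and the error is about 5% whenever sizes or SDs match. These are scenario values, not estimates for this study.

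The case for reporting intervals does not depend on unequal variances: at 15 against 30, differences well short of 0.91 SD would often go undetected. The consequence is confined to describing enrollment factors in a formative pilot. The comparison of treatment-initiation rates is unaffected.

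**What to change.** In the SAP's Data Analysis paragraph, and in the matching protocol sentence under A4c, replace Student's t-test with Welch's t-test. Lead with the estimated difference between agreers and decliners (standardized if wished) and its 95% CI, and state that non-significance is not evidence of similarity. Adding an exact test for sparse categorical tables is optional.

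The cost is one line of text and no new data. The statistical price, if the SDs are in fact equal, is about 1 point of power at 15 against 30; it grows somewhat as the groups become more unequal.
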